## 1. Background

An important observation that has emerged from the global COVID-19 pandemic has been that men have a more severe course and higher mortality following infection with SARS-CoV-2 (Cao et al., 2020; Zhou et al., 2020). This gender disparity was also seen in the previous SARS and MERS outbreaks (Alghamdi et al., 2014; Karlberg et al., 2004; Leong et al., 2006). All three of the pathogens share a unique requirement for activation by the trypsin-like serine protease TMPRSS2 for infectivity and viral spread (Hoffmann et al., 2020a). TMPRSS2 has been demonstrated to proteolytically process and prime the S protein to mediate viral entry into host cells and is essential for viral spread and pathogenesis, making it a prime target for treatment (Hoffmann et al., 2020). Two strategies for blocking TMPRSS2 activity are (1) to inhibit proteolytic activity and (2) to downregulate expression of the protein. We hypothesize that a combination of these two strategies together would improve outcomes compared to Camostat alone or standard of care without either of these two drugs.

### 1.1. Camostat

[figure not shown]
Camostat mesilate is a serine protease inhibitor. It is approved for use in Japan for the treatment of chronic pancreatitis and reflux esophagitis (ONO Pharmaceutical, 2009). It has been shown in vivo to inhibit TMPRSS2 thereby blocking viral entry into host cells (Hoffmann et al., 2020a). In similar disease of SARS, caused by SARS-CoV, which uses similar mechanism of entry, camostat treatment also improved survival times in a mouse model of SARS-CoV infection (Zhou et al., 2015). We hypothesize that inhibition of TMPRSS2 with camostat, by treating early in the disease course when patients are diagnosed as outpatients, will decrease the percentage of people who end up hospitalized from COVID-19.

### 1.2. Bicalutamide

TMPRSS2 is an androgen regulated transmembrane serine protease that is highly expressed in prostate cells, which have the highest expression of this protein in humans. TMPRSS2 is also expressed in other tissues including the lung and gastrointestinal tract. While we do not have direct evidence of antiviral activity of bicalutamide against SARS-CoV-2, the rationale for using bicalutamide in patients infected with SARS-CoV-2 is based on strong scientific rationale and safety data as described in detail below. In brief, our hypothesis is that the SARS-CoV-2 must be proteolytically processed by a human protease known as TMPRSS2. Inhibition or blocking expression of TMPRSS2 inhibits SARS-CoV-2 infection. The expression level of the TMPRSS2 protease is regulated by androgen. Treatment with an antiandrogen such as bicalutamide downregulates expression of TMPRSS2. This downregulation should reduce proteolytic activation of SARS-CoV-2 and help to limit severity of infection and subsequent morbidity and mortality.

Recent experimental data has demonstrated that the human protease Transmembrane Serine Protease 2 (TMPRSS2) plays an important role in COVID-19 infection. Hoffman et al demonstrated that TMPRSS2 proteolytic activity is able to prime the spike protein (S protein) of SARS-CoV-2 (Hoffmann et al., 2020a). Proteolytic priming by TMPRSS2 allows for binding of the virus to the angiotensin-converting enzyme 2 (ACE2) as the entry receptor. TMPRSS2 is also capable of activating Influenza A and B, MERS and SARS-CoV (Böttcher et al., 2006; Matsuyama et al., 2010). Hoffman et al demonstrated that cells lacking TMPRSS2 expression were less susceptible to SARS-CoV-2 infection and inhibition of TMPRSS2 proteolytic function could block SARS-CoV-2 infection (Hoffmann et al., 2020a).

TMPRSS2 is highly expressed by human prostate tissue but is also expressed by many normal human epithelial cells including the colon, stomach and lung (Bertram et al., 2012; Lin et al., 1999; Lucas et al., 2008, 2014; Mikkonen et al., 2010). Previous studies demonstrated that TMPRSS2 is an androgen-regulated gene whose expression could be downregulated by androgen withdrawal and antiandrogens, **Figure 1A, B** (Bühler et al., 2010; Lin et al., 1999; Semaan et al., 2019).

[figure not shown]

**Figure 1.** TMPRSS2 expression is downregulated by antiandrogens.

(A) Bicalutamide induces a 7-fold decrease in expression of TMPRSS2 in human AR-positive LNCaP prostate cancer cell line. (Bühler P, et al. Urol Int. 2010;84(2):203-11.)

(B) The antiandrogen enzalutamide induces marked down-regulation of androgen regulated genes PSA and TMPRSS2 in human AR-positive VCaP prostate cancer cell line. (Semaan L, et al. BMC Cancer. 2019 Oct 21;19(1):972.)

Mikkonen et al demonstrate the presence of androgen receptor expression in murine lung tissue from both male and female mice and in a human lung cancer cell line (Mikkonen et al., 2010). Androgen exposure in this lung cancer line cell line resulted in an ~ 3-fold increase in expression of TMPRSS2, **Figure 2A**. Bertram et al further demonstrated strong TMPRSS2 expression in both human lung epithelium and human sinus, **Figure 2B** (Bertram et al., 2012).

[figure not shown]

**Figure 2.** (A) Androgen receptor expression in murine lung from castrate male mice and female mice. AR expression is increased in both castrated male and female mice in response to androgen (From Mikkonen et al Mol Cell Endocrinol. 2010 Apr 12;317(1-2):14-24.); (B) TMPRSS2 is expressed in human lung and sinus (From Bertram et al. PLoS One. 2012;7(4):e35876)

Anti-androgens, such as bicalutamide, effectively downregulate expression of the TMPRSS2 in the normal prostate and prostate cancer cells and other tissues. TMPRSS2 is also

downregulated in the prostate by estrogen receptor beta (ER- beta) stimulation by estrogens (Setlur et al., 2008; Tomlins et al., 2005). Bicalutamide is an oral non- steroidial antiandrogen that downregulates TMPRSS2. It is well tolerated, widely available, and inexpensive. It is currently FDA approved for the treatment of prostate cancer and has also been used in women for the treatment of hirsutism, polycystic ovarian disease, and breast cancer (Gucalp et al., 2013; Moretti et al., 2018).

Additionally, ACE2 receptor is located on the X-chromosome and also escapes X inactivation (Gheblawi Mahmoud et al., 2020). Previous research found that ACE2 is primarily expressed in the kidney where there is greater activity in the male kidney compared to females. (Liu et al., 2010) More recently, it has also been demonstrated that in the lung, where ACE 2 is also expressed albeit at lower levels, estradiol downregulates ACE2 expression as seen in **Figure 3**. (Stelzig et al., 2020)

**Figure 3.** Angiotensin-converting enzyme 2 (ACE2) mRNA expression in normal human bronchial epithelial cells demonstrating reduced expression with the treatment of estradiol. The quantities of ACE2 were normalized against that of ribosomal protein S16 mRNA. \*P<0.05 by 2-tailed Student's *t* test. (From Stelzig et al. Am J Physiol Lung Cell Mol Physiol 318: L1280-L1281, 2020).

[figure not shown]
Since AR, and ER are also expressed in lung tissues, we hypothesize that these receptors, through regulation of TMPRSS2 expression, may contribute to the higher morbidity and mortality among men with COVID-19. In prostate cancer patients, bicalutamide effectively downregulates expression of the androgen regulated serine protease Prostate-Specific Antigen (PSA). Decline in PSA following bicalutamide therapy is used as a biomarker of efficacy in men with prostate cancer.

A second important component is regulation of the host immune response to SARS-CoV-2 infection as this is likely to be a major contributor to COVID-19 disease manifestations (Chen et al., 2020). Progression of the disease to late stages including pneumonia and acute respiratory distress syndrome (PNA-ARDS) appears to exhibit characteristics similar to many forms of viral mediated PNA- ARDS, including unremitting lung inflammation and tissue injury that can be disproportionate to pathogen load at late stages. There is published literature showing regulation of Treg numbers and activity by estrogens and Estrogen Receptor (ER) (Tai et al., 2008), promoting activity to suppress inflammatory damage. In strong preliminary data from the labs of team members Drs. [name] and [name], these effects were mediated by ER-beta, and use of the estrogen Estradiol (E2) or selective ER-beta agonists led to

significant Treg amplification and pro-repair functions to strongly accelerate resolution of ARDS in a murine pneumonia model. Bicalutamide, is an anti-androgen that crosses the blood brain barrier inhibiting AR in the hypothalamus (unpublished data). This leads to a feedback release of LHRH that leads to increased levels of pituitary LH stimulating subsequent increased production of testosterone by the testes which is subsequently aromatized to estradiol. Androgen receptor signaling has known effects on many antiviral immune responses, including type 1 IFN activity, CD8+ T cell frequencies, subsets of CD4+ T cells, including Tregs, and humoral immunity. We hypothesize that these estrogenic effects in enhancing the immune response may also mediate some of the sex differences in COVID-19 PNA-ARDS and treatment with bicalutamide would improve outcomes.

Notably, we are including women. While men have a more severe course and higher mortality, women still are suffering and dying from SARS-CoV-2 infection. We do think that the proposed mechanism of benefit is applicable to both men and women for the following reasons:

[figure not shown]
(1) TMPRSS2 and ACE2, are expressed in the lung epithelial tissue of both men and women, albeit at varying levels. Asselta et al used genotype tissue expression (GTEx database (<https://gtexportal.org/home/>) and Gene Expression Omnibus (GEO) repository (<https://www.ncbi.nlm.nih.gov/geo/>) and showed that TMPRSS2 expression is also present in women, albeit at lower levels in women compared to men (Figure 4).

**Figure 4.** (A) ACE2 and (B) TMPRSS2 expression mRNA expression levels in human normal lung samples, stratified by sex (From Asselta, et al. *Aging*. 2020 Jun 5;12(11):10087-10098).

[figure not shown]
(2) The androgen receptor is also expressed in men and women at varying levels. Previous studies demonstrated that TMPRSS2 is an androgen-regulated gene whose expression could be downregulated by androgen withdrawal and antiandrogens (Bühler et al., 2010;

Lin et al., 1999; Semaan et al., 2019). Mikkonen et al demonstrate the presence of androgen receptor expression in murine lung tissue from both male and female mice and in a human lung cancer cell line (Mikkonen et al., 2010). Androgen exposure in this lung cancer line cell line resulted in an ~ 3-fold increase in expression of TMPRSS2, **Figure 5A**.

**Figure 5.** (A) Androgen receptor expression in murine lung from castrate male mice and female mice. AR expression is increased in both castrated male and female mice in response to androgen (From Mikkonen et al 2010)

(3) There is significant heterogeneity in levels of circulating androgens in women across age groups, albeit at lower levels than men. We hypothesize that the reason women do not have such severe disease is due to lower levels of circulating androgens compared to men (**Figure 6**). This subsequently affects TMPRSS2 levels and viral spread. However, women do have androgens, at variable levels, throughout the lifespan (Khosla et al., 1998) and therefore, would potentially also perceive benefit from treatment with an anti-androgen.

**Figure 6.** Testosterone levels in men (square) are higher than in women (circles), and present even in older women. (From Khosla, 1998).

(4) There is no justifiable reason to exclude them as bicalutamide has been used in women, at this dose, with no new safety signals. In terms of risk-benefit, bicalutamide has been given to women in clinical studies for treatment of hirsutism, particularly in the context of

polycystic ovarian syndrome, a dysmetabolic disorder that occurs in women due to excess androgen levels (Azziz et al., 2016). The major side effects noted were in the context of long term exposure, and risk to women should be greatly mitigated in this study due to the short course of exposure (7 days). Additionally it has been studied, at the dose of 150mg daily, for the treatment of androgen receptor (AR) positive triple negative breast cancer. In a phase II study by Gucalp et al, 426 patients were screened and 28 had AR+ disease and started treatment. There were no grade 4 of 5 events. There were 3 grade 3 liver related adverse events (AST elevation, hyperbilirubinemia, and alk phos elevation) and these all occurred in a single patient who known liver metastases and disease progression. Two patients had dose delays due to liver function test grade 2 abnormalities and these also were related to cancer progression. One patient had a dose reduction due to cerebrovascular ischemia that was thought to be related to hypertension and she continued on therapy (Gucalp et al., 2013). Thus, even in this sick patient population with metastatic breast cancer, bicalutamide, at this dose, did not demonstrate any unexpected or severe side effects in women.

## 2. Objectives

### 2.1. Primary objective

To determine if bicalutamide + camostat decreases the rate of hospitalization in outpatients diagnosed with COVID-19.

### 2.2. Secondary objectives

To determine if bicalutamide + camostat:

- Decrease the proportion of people with symptoms at day 7 and day 21
- Are safe to give in outpatients with COVID-19
- Decrease all-cause mortality at 60 days

### 2.3. Exploratory objectives

To determine if bicalutamide + camostat:

- Decrease the duration of hospitalization (defined as number of calendar days in the hospital)
- Decrease the % of patients needing upgrade to the intermediate care unit (IMC)
- Decrease the duration of IMC stay
- Decrease the % of patients needing upgrade to the intensive care unit (ICU)
- Decrease the duration of ICU stay
- Decrease the need for mechanical ventilation
- Decrease the duration of mechanical ventilation
- Alter development of SARS-CoV-2 antibodies
- Alter systemic cytokine profiles
- Alter hormone levels

### 2.4. Primary endpoint

Percentage of people who are hospitalized or die by day 28.

### 2.5. Secondary endpoints

- Proportion of people with symptoms at day 7 and day 21

- Proportion of drug-related AEs and SAEs
- All-cause mortality at day 60

## 2.6. Exploratory endpoints

Attenuation in disease course/inflammatory response –*resources permitting*

- Change from baseline in white blood cells, platelets, D-dimer, AST, ALT, CK, CRP, ESR, ferritin
- Change from baseline in hormones and hormone regulated gene expression
- Immunophenotyping of PBMCs with fluorescence-activated cell sorting (FACS): to understand the immune response and to determine the source of critical cytokines (resources permitting)
- SARS-CoV-2 antibody analysis, including IgM to IgG transition and virus-neutralizing antibodies

Clinical exploratory endpoints

- Duration of hospitalization (defined as number of calendar days in the hospital)
- % of patients needing upgrade to the intermediate care unit (IMC)
- Duration of IMC stay
- % of patients needing upgrade to the intensive care unit (ICU)
- Duration of ICU stay
- % of patients with need for mechanical ventilation
- Duration of mechanical ventilation

## 3. Patient Selection

A total of 40 patients will be recruited.

### 3.1. Inclusion Criteria

1.  $\geq 60$  years of age
2. COVID-19 infection, confirmed by polymerase chain reaction (PCR) test  $\leq 5$  days from enrollment done in the ambulatory setting
3. Able to provide informed consent
4. Symptom related to COVID-19. This includes: fever or chills, cough, shortness of breath or difficulty breathing, fatigue, muscle or body aches, headache, new loss of taste or smell, sore throat, congestion or runny nose, nausea or vomiting, diarrhea or other symptom recognized by the Centers for Disease Control to be a symptom of COVID-19.

### 3.2. Exclusion Criteria

1. Patients who undergo asymptomatic screening test that is positive and remain asymptomatic during the eligible time window
2. Patients who have had one or more positive tests more than 5 days prior to enrollment but within 60 days of enrollment (ex. If a patient has a positive test 10 days prior to enrollment and then a second positive test the day referred for enrollment, that patient would be excluded. If a patient had a positive test 5 months ago, and then another positive test the day he/she was referred for enrollment, that patient would be eligible.)
3. Unable to take oral medication

4. Male patients with female partners of reproductive potential who are unable to maintain effective contraception during the recommended time period (during treatment and for 130 days after the final dose)
5. Symptoms requiring hospitalization or immediate referral to hospital
6. Taking bicalutamide, any systemic hormonal therapy, or camostat within one month of study entry
7. Known hypersensitivity to bicalutamide, or camostat, or its components.
8. On coumadin anticoagulation (because of drug-drug interaction with bicalutamide)
9. Self-reported past medical history of chronic liver disease or cirrhosis
10. Self-reported myocardial infarction within 6 months or past medical history of congestive heart failure with known ejection fraction < 40%
11. Taking any other investigational treatment for COVID-19 or COVID-19 prophylaxis (COVID-19 vaccines and treatments allowed under FDA Emergency Use Authorization are allowed.)

[figure not shown]
### 3.3. Inclusion of Women and Minorities

Women and people from all ethnic and race groups are eligible for this study.

## 4. Treatment Plan

### 4.1. Study design

This will be a randomized, open-label study to determine if camostat+ bicalutamide decreases the proportion of people with COVID-19 who require hospitalization, compared to historical controls. Patients with symptomatic COVID-19, diagnosed as outpatients, will be randomized 1:1 stratified by gender and receipt of SOC drugs/vaccine, to treatment with standard of care alone or with camostat+bicalutamide . The schema is shown below:

### 4.2. Study treatments

#### 4.2.1. Camostat and Bicalutamide

Patients randomized to camostat and bicalutamide arm will receive 600mg of camostat mesilate (six 100mg tablets), four times a day on an empty stomach [one hour before a meal (e.g. 6:00, 11:00, 16:00, and 21:00)] and 150mg of bicalutamide daily for a total of 7 days. Bicalutamide will be given as three 50mg tablets.

Rationale for dose: Bicalutamide is well tolerated at 50mg and 150mg. It is frequently given at a dose of 150mg when used as a single agent, rather than the 50mg dose which is usually given in combination with medical or surgical castration. Bicalutamide 150mg

daily is approved for use in the European Union for the treatment of prostate cancer (European Medicines Agency, 2018). Bicalutamide has been extensively tested at a higher dose of 150 mg per day as monotherapy for prostate cancer, although it is not FDA-approved at this dose. Pharmacokinetic studies demonstrate an approximate doubling of the Cmax, Css and AUC and when bicalutamide is administered at this 3-fold higher dose.(Cockshott, 2004) Thus, we are using the higher dose bicalutamide of 150 mg/day compared to lower dose of 50 mg/day in order to achieve maximum androgen receptor blockade over the short 7-day exposure period proposed in this trial

Should any patient enrolled on the study miss a scheduled dose for whatever reason, the patient will be allowed to take the scheduled dose up to a maximum of 12 hours after that scheduled dose time. If greater than 12 hours, the missed dose should not be taken and the patient should take their allotted dose at the next scheduled time. Patients should also be advised to avoid conceiving for 3 months after the last dose of bicalutamide.

Rationale for duration of bicalutamide and camostat:

Both drugs are generally used for long periods of time, with bicalutamide safely given for years at a time. Trough concentrations of 150 mg/day bicalutamide at 7 days exceed the steady state trough levels of 50 mg/day bicalutamide after 28 days. Additionally, an increase in estradiol has been demonstrated at one week of starting bicalutamide at this dose. (Verhelst et al., 1994)

Additionally, respiratory infections are commonly treated for up to 7 days. For example, the Infectious Disease Society of America (IDSA) guidelines for the recommendation of treatment of influenza is for 5 days of anti-viral therapy in outpatients, with consideration of longer duration for certain populations. Given this trial is in patients at least 60 years old and the severity of the disease, we believe a longer duration is warranted. This, in combination with the data presented above, is why we believe 7 days is safe, likely to be effective, and in line with other treatment paradigms.

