### 5. Dosing Delays/Dose Modifications

If patients are unable to tolerate 600mg of camostat four times a day, the dose will be reduced to 300mg four times a day. If patients are unable to tolerate 300mg four times a day, treatment will decrease to 200mg three times a day (approved dose in Japan). If patients are unable to tolerate that dose, treatment will be stopped.

If patients are unable to tolerate 150mg of bicalutamide, the daily dose will be reduced to 100mg. If patients are unable to tolerate 100mg, the dose should be reduced to 50mg. If 50mg is unable to be tolerated, treatment should stop.

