### ***Camostat***

There is no known information on overdose of camostat.

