## PHARMACOLOGY

### 1. Blood concentration

(1) Healthy adults When a single dose of camostat mesilate at 200 mg was orally administered to 5 healthy adults in the fasted state, the plasma concentration of its active metabolite, 4-(4-guanidinobenzoyloxy) phenylacetate, reached a maximum of 87.1 ng/mL 40 minutes after administration, with a half-life of about 100 minutes (Hiraku S. et al.: Iyakuhin Kenkyu, 13: 756, 1982.).

(2) Patients with gastrectomy: When a single dose of camostat mesilate at 100 mg was orally administered to 4 patients with total gastrectomy or subtotal gastrectomy in the fasted state, the maximum plasma concentration was 30 ng/mL, changing at a similar level to healthy volunteers. (Yamamoto T. et al.: Changes in plasma concentration of camostat mesilate in patients with gastrectomy. Internal data of Ono Pharmaceutical Co., Ltd)

2. Metabolism: Carboxylate ester moiety of camostat mesilate is hydrolyzed to an active metabolite 4-(4-guanidinobenzoyloxy) phenylacetate, which is further hydrolyzed to 4-guanidinobenzoic acid. (Ohki S. et al.: Gendai Iryo, 12 (Extra issue): 71, 1980.) Camostat mesilate is mainly hydrolyzed by carboxyesterase and 4-(4-guanidinobenzoyloxy) phenylacetate by arylesterase (in vitro). (Nemoto H. et al.: The enzymes involved in the metabolism of camostat mesilate. Internal data of Ono Pharmaceutical Co., Ltd.) Camostat mesilate and its metabolite 4-(4-guanidinobenzoyloxy) phenylacetate did not inhibit CYP1A2, CYP2C9, CYP2C19, CYP2D6 and CYP3A4 (in vitro). (Matsunaga N. et al.: The effect of camostat mesilate on CYP 450 isozymes. Internal data of Ono Pharmaceutical Co., Ltd)

3. Excretion: When a single dose of camostat mesilate at 200 mg was orally administered to 5 healthy adults in the fasted state, urinary metabolites were accounted for mostly by 4-guanidinobenzoic acid and for only a small proportion, by 4-(4-guanidinobenzoyloxy) phenylacetate. The rates of urinary excretion at 5 - 6 hours after administration were 20% and 0.8%, respectively, and little was further recovered in urine during later periods. (Hiraku S. et al.: Iyakuhin Kenkyu, 13: 756, 1982)

4. Protein binding rate: The protein-binding rate to human serum was 25.8 – 28.2% (in vitro).

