#### 8.2. Bicalutamide

Bicalutamide tablets contain 150 mg of bicalutamide, a non-steroidal androgen receptor inhibitor with no other known endocrine activity. The chemical name is propanamide, N [4 cyano-3- (trifluoromethyl)phenyl]-3-[(4-fluorophenyl)sulfonyl]-2-hydroxy-2-methyl-, (+). The structural and empirical formulas are:

Bicalutamide has a molecular weight of 430.37. The pKa is approximately 12. Bicalutamide is a fine white to off-white powder which is practically insoluble in water at 37°C (5 mg per 1000 mL), slightly soluble in chloroform and absolute ethanol, sparingly soluble in methanol, and soluble in acetone and tetrahydrofuran. CASODEX is a racemate with its antiandrogenic activity being almost exclusively exhibited by the R-enantiomer of bicalutamide; the S-

enantiomer is essentially inactive. The inactive ingredients of CASODEX tablets are lactose, magnesium stearate, hypromellose, polyethylene glycol, polyvidone, sodium starch glycollate, and titanium dioxide.

Bicalutamide is a non-steroidal androgen receptor inhibitor. It competitively inhibits the action of androgens by binding to cytosol androgen receptors in the target tissue. In clinical trials with bicalutamide as a single agent for prostate cancer, rises in serum testosterone and estradiol have been noted.

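### The single 12-hour missed-dose rule in Section 4.2.1 fits once-daily bicalutamide but lets four-times-daily camostat doses be stacked, and Section 8.2 contradicts the 50 mg bicalutamide tablet

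*Combined protocol and SAP*

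**What the plan says.** Section 4.2.1 gives camostat 600 mg "four times a day on an empty stomach [one hour before a meal (e.g. 6:00, 11:00, 16:00, and 21:00" and bicalutamide 150 mg once daily, both for 7 days. One missed-dose rule follows. It opens "Should any patient enrolled on the study miss a scheduled dose for whatever reason" and continues "the patient will be allowed to take the scheduled dose up to a maximum of 12 hours after that scheduled dose time". A dose more than 12 hours late is dropped and the patient resumes at the next scheduled time. No other limit on a late dose is stated.

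Section 5 covers dose reduction for intolerance: camostat goes to 300 mg four times a day, and then "treatment will decrease to 200mg three times a day (approved dose in Japan"). Section 6.11 defines overdose in general terms, sets no threshold in mg, and requires every overdose to be reported as an SAE. On camostat it says: "There is no known information on overdose of camostat".

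On tablet strength, Section 4.2.1 says "Bicalutamide will be given as three 50mg tablets". Section 8.2 opens with "Bicalutamide tablets contain 150 mg of bicalutamide", and its Route of Administration line tells patients to take a single 150 mg tablet each day. The Formulation line of the same section gives 50 mg.

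**The concern.** A 12-hour grace period is half the dosing interval for a once-daily drug, and more than the whole interval for camostat. A patient who forgets the 6:00 dose and remembers at 11:00 is told, in effect, that the late dose may still be taken and that the 11:00 dose is also due. The text does not say which instruction gives way.

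Dosing is at home, in patients aged 60 or over, with six camostat tablets four times a day on an empty stomach, so late doses are likely. The protocol has no overdose information for camostat. Section 8.1 lists severe hyperkalaemia and hepatic disorder among its significant reactions and advises electrolyte monitoring, but the study laboratory tests are optional (Sections 6.4 and 10). Because Section 6.11 makes every overdose an SAE, sites could also classify the same permitted double dose differently, and drug-related SAEs are a secondary endpoint.

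The tablet discrepancy is a separate, smaller matter. Site staff reading Section 8.2 would find a strength and a tablet count that differ from what Section 4.2.1 dispenses.

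**Working it through.** **Inputs.** Camostat 600 mg at 6:00, 11:00, 16:00 and 21:00; bicalutamide once daily; window 12 hours; duration 7 days (Section 4.2.1). Approved camostat regimen 200 mg three times a day (Section 5). Active metabolite "with a half-life of about 100 minutes" (Section 8.1, Pharmacology). The protocol gives no calculated figure here to reproduce.

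**Step 1: later doses inside each window.**

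| Missed dose | Gap to next | Window closes | Later doses inside |
|---|---|---|---|
| 6:00 | 5 h | 18:00 | 11:00, 16:00 |
| 11:00 | 5 h | 23:00 | 16:00, 21:00 |
| 16:00 | 5 h | 04:00 | 21:00 |
| 21:00 | 9 h | 09:00 | 06:00 |

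Over 7 days there are 4 × 7 = 28 doses. All but the last have a later dose in their window, so 27 of 28. On an even 6-hourly schedule every daily slot's window reaches two later doses, so the result does not depend on the example times. For bicalutamide, 0 of 7 windows reach the next dose.

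**Step 2: most that may be taken at once.** At 6:00 or 11:00, two doses are open together: 2 × 600 = 1,200 mg. At 16:00 (6:00 and 11:00 missed) or 21:00 (11:00 and 16:00 missed), three are: 3 × 600 = 1,800 mg. Relative to the approved 200 mg single dose: 600/200 = 3 (planned), 1,200/200 = 6, 1,800/200 = 9. The cumulative dose stays at or below 2,400 × 7 = 16,800 mg.

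**Step 3: reduced regimens.** Two 300 mg doses together make 600 mg, the dose such a patient has already failed to tolerate. At 200 mg three times a day, assuming 8-hour spacing, the 12-hour window contains the next dose; two together make 400 mg, above the 300 mg already not tolerated.

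**Step 4: rough effect on peak level.** Assume first-order elimination, dose proportionality and an instantaneous peak. The fraction left after t minutes is 2^(−t/100): 2^(−3) = 12.5% after 5 h and 2^(−5.4) = 2.4% after 9 h. In units of one dose, the on-schedule peaks are about 1.03 (6:00), 1.13 (11:00) and 1.14 (16:00 and 21:00). Examples against the usual peak at the same time of day:
- 21:00 dose taken with 6:00: 2.00/1.03 ≈ 1.95
- 11:00 dose taken with 16:00: 2.02/1.14 ≈ 1.77
- 6:00 and 11:00 doses taken with 16:00: 3.00/1.14 ≈ 2.63

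So two doses together give about 1.8 to 2.0 times the usual peak, and three about 2.6 times.

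**Step 5: tablets.** One 50 mg tablet taken under a one-tablet instruction gives 50/150 = one third of the dose; three 150 mg tablets would give 450 mg. The Section 5 reductions to 100 mg and 50 mg need 50 mg tablets, which supports Section 4.2.1 and the Formulation line.

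**The case against.** The strongest reply is that the protocol never instructs anyone to double. It allows a late dose and is silent about the next one, and the rule sits among text about bicalutamide, so it may have been written with that drug in mind. Many patients would not swallow 12 tablets together, let alone 18, and the 1,800 mg case needs two consecutive misses. This is fair about likelihood. It does not remove the problem: the section covers both drugs, the rule applies to any scheduled dose, and a patient who doubles has broken no instruction.

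The peak multiples deserve caution. The half-life comes from a single 200 mg dose in 5 fasted healthy adults, and the same source puts the maximum at 40 minutes, so an instantaneous peak is a simplification. No passage links peak level to harm. The multiples are therefore only indicative; the finding rests on the dose counts in Steps 1 and 2.

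There are safeguards: a treatment diary, calls on days 3 and 7, pill reconciliation, SAE reporting and DSMB review. They mostly detect doubling after it has happened. The diary is not in the documents and may carry clearer instructions, so no error in it is claimed.

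On tablets, Section 8.2 contradicts itself rather than being wrong throughout, and the intended 150 mg daily dose is the same everywhere. That makes it a correction of wording, but one of the wrong lines is a direct patient instruction.

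**Conclusion.** The concern holds. As written, the rule permits two camostat doses together (1,200 mg) after a single miss at any daily slot except the final dose of the course, and three together (1,800 mg) at 16:00 or 21:00 after two consecutive misses. The clock pattern depends on the example times; the overlap itself arises on an even 6-hourly schedule too. The increase in peak, about 1.8 to 2.0 times or 2.6 times, rests on the pharmacokinetic assumptions in Step 4. Cumulative exposure is not increased.

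The tablet inconsistency in Section 8.2 also holds. Both points should be fixed, but neither threatens the trial's inference: about 20 patients are treated for 7 days, and sample size, power and analysis do not change.

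**What to change.** In Section 4.2.1, limit the 12-hour rule to bicalutamide and add a camostat rule along these lines: *A missed camostat dose may be taken up to X hours late; after that, or once the next dose is due, skip it. Never take two doses together.* The investigator should set X below 5 hours. For illustration, X = 2 leaves at least 3 hours to the next dose, when 2^(−1.8) ≈ 29% of the late dose remains; X = 1 leaves about 19% and X = 3 about 44%, on the Step 4 assumptions. State that the rule also covers the reduced camostat regimens in Section 5.

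In Section 8.2, change the opening line to 50 mg tablets and the Route of Administration line to three 50 mg tablets once daily. While editing, align the 3-month conception advice in Section 4.2.1 with the 130 days in Sections 3.2 and 8.2 (about 90 against 130 days, 40 days short). This is minor in a population aged 60 or over.

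The cost is a short protocol clarification and a check that the diary and dispensing instructions match. The one trade-off is that some late camostat doses will be skipped, which slightly lowers total exposure in patients who miss doses.
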